***Step 2: MI regression;**

```
PROC MI data=step1 out=step2 seed=192185 nimpute=5;  
  var trt invid age sexn nrace fstn v1 v2 v3 v4 v5;  
  monotone reg(v2 = trt invid age sexn nrace fstn v1); *for missing at v2;  
  monotone reg(v3 = trt invid age sexn nrace fstn v1 v2); *for missing at v3;  
  monotone reg(v4 = trt invid age sexn nrace fstn v1 v2 v3); *for missing at v4;  
  monotone reg(v5 = trt invid age sexn nrace fstn v1 v2 v3 v4); *for missing at v5;  
run;
```

The imputed values will be round to integer and within the range of 0 to 4.

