5.2 Handling of Dropouts or Missing Data

For demographics, baseline characteristics, safety profile and other evaluations, each variable will be analyzed using the existing data. Subjects with missing data will be excluded only from the analyses for which data are not available.

No missing values will be replaced in the PP analyses. There will not be missing data for the primary efficacy endpoint for the PP population based on the PP definition in Section 4.

Only for the overall LFGS and its derivatives for the mITT analysis, missing scores will be replaced using the multiple imputation (MI) approach for the mITT analysis only. Depending on the pattern of missingness, a two-step process may be employed. If missing data occur for an intermediate visit, they will be imputed first via a Markov Chain Monte Carlo (MCMC) method. As a result, a monotone missingness pattern will be obtained for the data to be fully imputed. The subsequent imputation will use Monotone Regression to produce 5 imputed datasets where the remaining missing data are filled in.

When missing overall LFGS score at a given visit is imputed, the values from all its previous visits will be included as predictor in the imputation model. For example, for a subject with missing overall LFGS at Visit 4, the overall LFGS scores from Visits 1 through 3 for the subjects will be included in the imputation model. Other variables that go into the imputation models include treatment, site, and key baseline characteristics of age, gender, race and Fitzpatrick skin type.

To prepare for MI, for subjects who are early discontinued from the study, their efficacy data captured at the termination visit will be assigned to the nearest corresponding scheduled visit.

The SAS code for MI is as follows, using the random number 69833 as the seed for the first Step and 192185 as the seed for the second step. Where notation of main variables:

- Trt = treatment: 1 for Test product, 2 for competitor product
- Invid = site number
- Age = subject's age

- Sexn = gender: 1 for female, 2 for male
- Nrace = race: 1 for White, 2 for Asian, 3 for Native Hawaiian or Other Pacific-Islander, 4 for Black or African American, 5 for American Indian or Alaska Native, 6 for Other, 7 for Mixed
- Fstn = Fitzpatrick skin type in numeric value
- v1 - v5: LFGS at Visits 1-5 accordingly

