***Step 1: MCMC fills interim missingness to make monotone;**

```
PROC MI data=eff out=step1 seed=69833 nimpute=1;  
  mcmc impute=monotone;  
  var trt invid age sexn nrace fstn v1 v2 v3 v4 v5;  
run;
```

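### The SAP's imputation code gives site number and the unordered race code one straight-line slope each, so the imputed mITT lip-fullness scores depend on arbitrary labels

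*SAP*

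**What the plan says.** SAP Section 5.2 restricts imputation to the overall LFGS and its derivatives in the mITT analysis. Besides the LFGS scores from previous visits, it names the predictors: "Other variables that go into the imputation models include treatment, site, and key baseline characteristics of age, gender, race and Fitzpatrick skin type".

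The variable list then defines site as "Invid = site number" and race as "Nrace = race: 1 for White, 2 for Asian, 3 for Native Hawaiian or Other Pacific-Islander, 4 for Black or African American", continuing "5 for American Indian or Alaska Native, 6 for Other, 7 for Mixed".

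Step 1 fills intermediate gaps with "mcmc impute=monotone" and the list "var trt invid age sexn nrace fstn v1 v2 v3 v4 v5". Step 2 is called with "PROC MI data=step1 out=step2 seed=192185 nimpute=5", repeats that list, and fits one linear regression per visit. For the primary visit it is "monotone reg(v3 = trt invid age sexn nrace fstn v1 v2); *for missing at v3". Neither call contains a CLASS statement, and Section 5.2 defines no indicator variables. Imputed values are afterwards rounded to whole grades from 0 to 4.

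Elsewhere the SAP treats site as categorical: Section 5.3 uses it as the class variable in a Kruskal-Wallis test, as a fixed factor in analysis of variance, and as the adjustment factor in the CMH test.

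**The concern.** Site number and race code are names, not quantities. Without a CLASS statement or indicators, PROC MI treats both as continuous and estimates one slope for each. The text leads the reader to expect that sites and races may differ freely in the imputation model; the code allows only a steady trend across the labels.

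Two things follow. The imputed scores change if the same sites or races are numbered differently, which nobody would want of a pre-specified analysis. And the site and race terms, as coded, represent little of any real difference between sites or races. Site differences are plausible here, because under protocol Section 7.6.1 each site has its own Treating and Evaluating Investigators.

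At stake are the mITT analysis of the primary endpoint and the mITT versions of three secondary endpoints: the Month 2 LFGS responder rate and the LFGS change to Month 3 and to Month 6. The mITT analysis is the check on whether exclusions from PP drive the non-inferiority result, so it should be sound even though it is supportive.

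**Working it through.** The plan gives no figure on this point to reproduce. The check has three parts.

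**1. What the code forces.** Let b be the slope on the race code. The fitted differences from White (code 1) are:

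- Asian: (2 − 1)b = b
- Black or African American: (4 − 1)b = 3b
- Mixed: (7 − 1)b = 6b

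These ratios hold whatever the data show. If sites are numbered 1 to 7, site 7 differs from site 1 by (7 − 1) = 6 site slopes. With class terms, site would use 7 − 1 = 6 parameters (5 with 6 sites) and race up to 7 − 1 = 6, instead of one each. Fitted values from a site class effect were checked and do not change on relabelling (largest difference about 1e-15).

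**2. How much of a site effect a line through arbitrary labels can hold.** If k site effects are exchangeable with respect to their labels, the expected squared correlation between the effects and the label is 1/(k − 1):

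- k = 7 (protocol synopsis, approximate number of sites): 1/6 = 16.7%
- k = 6 (SAP table shells): 1/5 = 20%

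Simulation gave 0.165 for k = 7 and 0.200 for k = 6. This describes the site term on its own. The models also contain the LFGS scores from previous visits, which carry part of any lasting site effect.

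**3. Size of the dependence on labels.** Only the 158 subjects and the 6 or 7 sites come from the documents. The rest is assumed: 8% to 20% of Visit 3 scores missing, between-site SD 0.2 to 0.4 grade, site effect either present or absent at Visit 2, and the Visit 3 regression with Visits 1 and 2 as predictors. Each data set was imputed under different random site numberings with the residual draw held fixed.

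| Quantity, one site numbering versus another | Result |
|---|---|
| Mean absolute change in an imputed score, before rounding | about 0.07 to 0.17 grade |
| Share of rounded imputed scores that change | about 7% to 17% |
| Change in the mITT mean difference | about 0.01 to 0.02 grade |

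The low end applies when the site effect is already visible at Visit 2, the high end when it is not.

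In subjects: 8% of 158 is about 13 and 20% is about 32. Then 0.07 × 12.6 ≈ 1 and 0.17 × 31.6 ≈ 5, so roughly one to five rounded scores per imputed data set would differ.

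Against the margins: 0.02 is 0.02/0.50 = 4% of the protocol's limit and 0.02/1.0 = 2% of the limit in SAP Section 5.5.1. The SAP tests a Hodges-Lehmann shift, not a mean difference, so this comparison shows scale only.

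**The case against.** The strongest reply is that nothing important depends on this. SAP Section 5.5.1 makes PP definitive and mITT supportive, Section 5.2 allows no imputation in PP, and Section 5.1 calls the secondary comparisons descriptive. The mITT statistic is a Hodges-Lehmann difference on whole-grade scores, which a shift of 0.02 in the mean would rarely move. All of that stands, and it sets the severity.

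The 20% missing rate is also pessimistic. The 80% in the sample-size sections is the share expected to meet PP criteria. PP also drops subjects for visit timing and protocol violations, many of whom will have a Visit 3 score, and termination-visit data are assigned to the nearest scheduled visit. This is why the range starts at 8%.

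Four stronger readings are tempting, and the documents do not support them:

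- **Most of any site effect is lost.** The 1/(k − 1) result concerns the site term alone. Scores from previous visits, rated by the same evaluator where possible (protocol Section 7.6), bring part of a lasting effect back.
- **The analysis is not reproducible.** Race codes and both seeds are fixed in the SAP, and no renumbering of sites is planned. The fault is arbitrariness.
- **Imputed scores typically move by a third of a grade or more.** Values of about 0.3 to 0.6 describe the spread over 40 numberings, not the shift between two.
- **The SAP promises adjustment for site and race.** It says only that they are among the predictors. One slope on a nominal label still falls short of that.

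Numeric coding of treatment and sex is harmless with two levels, and a linear term for Fitzpatrick type is defensible because the scale is ordered.

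**Conclusion.** The point holds as a mismatch between the SAP's description and its code, and it can be read directly from Section 5.2 without any assumption. Site and race enter both imputation steps as single slopes on arbitrary labels, so the imputed overall LFGS scores depend on the numbering.

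The size rests on the assumed missing rate and between-site SD. Within those ranges it is modest for individual scores and very small for the treatment contrast. A reader might infer that the non-inferiority conclusion is at risk. No case was found in which it changes, and the PP result cannot be affected. This is a minor code correction, worth making because the code is published, with fixed seeds, as the analysis to be run.

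**What to change.** - **Step 2:** add `class invid nrace;` and keep both variables as effects in each regression. Treatment and sex may stay numeric, and Fitzpatrick type may stay as an ordered number.
- **Step 1:** replace `invid` and `nrace` with 0/1 indicator variables, because the MCMC method treats every listed variable as numeric and a CLASS statement does not solve the problem there.
- **Sparse race codes:** state a pooling rule in advance, for example combining codes below a stated minimum count into one Other group, so that the models can be fitted.

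The cost is a few lines of SAS and extra model parameters: with 7 sites and all race codes in use, (6 − 1) + (6 − 1) = 10 more per regression, and fewer after pooling. No data collection or design change is needed. It should be done before database lock; afterwards it becomes a post hoc change to a pre-specified analysis.

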5.3 Demographics and Baseline Characteristics

Baseline and demographic characteristic variables (including age, sex, race, ethnicity, and Fitzpatrick skin type) will be tabulated using descriptive statistics. For each continuous variable, the summary will include the mean, standard deviation (SD), median, minimum and maximum. For each categorical variable, the summary will include frequencies and percentages.

Poolability of the data across study sites for key demographic and baseline characteristics (age, sex, Fitzpatrick skin type, race, Body Mass Index) will be assessed for the AT population. For age and Body Mass Index, one-way analysis of variance (ANOVA) will be performed with study site as the main factor. For Fitzpatrick Skin Type Classification (I-VI), nonparametric Kruskal Wallis test will be conducted with study site as the class variable. For sex, Pearson's Chi-square test, or exact test if more appropriate, will be performed.

Demographic and baseline characteristics will be summarized and compared for PP subjects versus non-PP subjects. For categorical variables, comparison will be performed using the Cochran-Mantel-Haenszel (CMH) test for general association adjusted for site. For continuous variables, comparison will be conducted using two-way analysis of variance model (ANOVA) with fixed factors of group and site, with respect to the original values if normality assumption is satisfied, or with respect to ranked values if otherwise.

Descriptive summary of racial distribution within Fitzpatrick Skin Type will provided for the AT subjects.

5.4 Subject Accountability

A summary of subject disposition will be provided for all subjects descriptively, including reason for discontinuation and analysis populations. Disposition of analysis populations will also be tabulated by study site.

5.5 Efficacy Variables

Key efficacy assessments include the following:

- LFGS: 0 = very thin, 1 = thin, 2 = moderately thick, 3 = thick, 4 = full
- POL: 0 = None (a mouth with no perioral lines), 1 = Mild (a mouth with a few shallow perioral lines), 2 = Moderate (a mouth with some moderate lines), 3 = Severe (a mouth with many deep lines or crevices)
- Subject Satisfaction with Lips using a visual analog scale (VAS) on a 100-mm scale from 0 = Very Unsatisfied to 100 = Very Satisfied
- Patient Global Aesthetic Improvement (pGAI) Score: 1=Worse, 2=No change, 3=Improved, 4=Much improved, 5=Very much improved
- Investigator Global Aesthetic Improvement (iGAI) Score: 1=Worse, 2=No change, 3=Improved, 4=Much improved, 5=Very much improved
- Swelling Assessment: 0 = None, 1 = Minimal, 2 = Mild, 3 = Moderate, 4 = Severe

All efficacy analyses will be performed for both the PP and mITT populations.

5.5.1 Primary Efficacy Analysis

The primary efficacy endpoint is change from baseline to Visit 3/Month 2 in overall LFGS. The null hypothesis to be tested is that the Test device is inferior to the Control device. The results for PP are considered as definitive and those for mITT as supportive.

Summary statistics (mean, SD, minimum, median, maximum) and 95% confidence interval (CI) for mean will be presented for the changes scores for each treatment.

Due to the fact that the change scores would only contain 5 possible values (0, 1, 2, 3, and 4), the normal distribution assumption is hardly attainable, and therefore, the nonparametric Hodges-Lehmann (HL) estimators will be employed to test the study hypothesis. The 95% confidence limits for the median differences between the two treatment groups (PN40082 minus Restylane Silk) will be derived using PROC NPARIWAY with the option for the HL estimators. If the lower limit is on or above -1.0, the null hypothesis will be rejected to support the claim that PN40082 is non-inferior to Restylane Silk.

For the mITT analysis, the above analysis will be carried out for each copy of the MI data sets. Then PROC MIANALYZE will be performed to account for the between and within variation in the multiply imputed data sets.

To assist an assessment for the consistency of the treatment effect among sites, summary of the primary endpoint will be presented by site for the primary population (i.e., the PP subjects).

The primary endpoint will also be analyzed for the following two subsets of the PP subjects: (1) subjects that have injection on one lip only, and (2) subjects that have injections on both lips.

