### 8.1 Analysis Populations

Intent-to-treat (ITT) (safety) population: All randomized subjects who received study device

Modified intent-to-treat (mITT): All randomized subjects who met the inclusion/exclusion criteria, were randomized, and received study device

Per-protocol (PP): All randomized subjects who met all inclusion/exclusion criteria; received study device, completed Visit 5 within the specified window; had LFGS score by the Blinded Evaluating Investigator at Visit 3/Month 2 within the specified visit window, and had no significant protocol violations that would affect the treatment evaluation

Efficacy analyses will be performed on the mITT and PP populations, with PP as the primary population and mITT supportive.

Safety analyses will be performed on the ITT population.

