### **8.5 Sample Size Determination**

For the PRO 2018-02 study, the primary variable is change from baseline to Month 3 in LFGS. The sample size was determined based on (1) both PN40082 and Restylane Silk having an equal mean value with a common standard deviation of 0.85 for change from baseline in LFGS, and (2) the non-inferiority limit of -0.50. The test:control ratio of 1:1 results in 126 (63:63) PP subjects at 90% power. Assuming 80% of randomized subjects meet the PP criteria, a total of 158 (79:79) subjects will be randomized to obtain 126 (63:63) PP subjects.

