3.2 Sample Size Determination

For the PRO 2018-02 study, the primary variable is change from baseline to Month 3 in LFGS. The sample size was determined based on: (1) both PN40082 and Restylane Silk having an equal mean value with a common standard deviation of 0.85 for change from baseline in LFGS, and (2) the non-inferiority limit of -0.50. The test:control ratio of 1:1 results in 126 (63:63) per-protocol (PP) subjects at power of 90%. A total of 158 subjects will be randomized to obtain 126 (63:63) PP subjects assuming that 80% of randomized subjects meet the PP criteria.

4 Populations To Be Analyzed

Three subject populations are defined as follows:

- (1) As-treated (AT) (safety population): All randomized subjects who received study device. AT subjects will be included in the safety analysis for the treatment they actually received.
- (2) Modified intent-to-treat (mITT): All randomized subjects who met the inclusion/exclusion criteria, and received study device.
- (3) Per-protocol (PP): All randomized subjects who met all inclusion/exclusion criteria; received study device; completed Visit 5/Month 6 within the specified window; had overall LFGS score by the Blinded Evaluating Investigator at Visit 3/Month 2 within the specified visit window; and had no significant protocol violations that would affect the treatment evaluation.

For the purpose of determining the PP status of the subject, "significant protocol violations" are any unforeseen events that occurred during the conduct of the trial that result in noteworthy study protocol violations that could have possibly interfered with the therapeutic administration of the treatment or the precise evaluation of treatment efficacy.

Efficacy analyses will be performed on the mITT and PP populations, with PP as the primary population and mITT supportive. Analyses of safety and other evaluations will be performed on the AT population.

5 Planned Analyses

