5.1 Methodological Considerations

SAS software (version 9.4 or higher) will be used for all data analyses and tabulations.

Two-sided hypothesis testing will be conducted for all inferential analyses. Resulting p-values less than 0.05 will be considered statistically significant. To control the overall error rate, a hierarchical approach will be applied. Upon the significance of the primary efficacy outcome, secondary endpoints will be analyzed and no adjustment to the p-values will be applied to multiple comparisons. For this non-inferiority study, the null hypothesis to be tested for all the secondary endpoints is that there is no difference between the two products, and all statistical comparisons for these endpoints will be considered descriptive (non-inferential).

No interim analyses are planned.

All the data points will be presented in subject data listings.

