Subjects Included in the Modified Intent-to-Treat (mITT) Population	0 (0%)	0 (0%)	0 (0%)
Subjects Included in the Per-Protocol (PP) Population	0 (0%)	0 (0%)	0 (0%)

Source: Listings 16.2.1.1

O:\Studies\Prolenium\SYM 2018-02\Biometrics\Programs\Tables\xxx.sas ran on Month Day, Year at hh:mm on data from Month Day, Year.

Table 14.1.2 – Subject Discontinuations by Reason for All Randomized Subjects

	PN40082	Restylane Silk	Total
Subjects Randomized	0	0	0
Number Completed Study	0 (0%)	0 (0%)	0 (0%)
Total Discontinued	0 (0%)	0 (0%)	0 (0%)
Reason Discontinued			
-- Subject or legal representative withdrew consent	0 (0%)	0 (0%)	0 (0%)
-- Subject's study device assignment was unblinded	0 (0%)	0 (0%)	0 (0%)
-- Significant protocol violation	0 (0%)	0 (0%)	0 (0%)
-- Subject became pregnant			
-- An AE occurs for which the subject or the investigator determines that it is in the subject's best interest to be discontinued	0 (0%)	0 (0%)	0 (0%)
-- Lost to follow-up	0 (0%)	0 (0%)	0 (0%)
-- Investigator discretion	0 (0%)	0 (0%)	0 (0%)
-- Other	0 (0%)	0 (0%)	0 (0%)

Source: Listing 16.2.1.2

O:\Studies\Prolenium\SYM 2018-02\Biometrics\Programs\Tables\xxx.sas ran on Month Day, Year at hh:mm on data from Month, Day, Year.

Table 14.1.3 – Subject Enrollment by Study Site

Site Number	Randomized	AT	mITT	PP	Completed	Discontinued
1	0 (0%)	0 (0%)	0 (0%)	0 (0%)	0 (0%)	0 (0%)
2						
3						
4						
5						
6						
Total	XX	XX	XX	XX	XX	XX

AT: As-Treated, mITT: Modified Intent-to-Treat, PP: Per-Protocol
Percentages are based on the total number of subjects in each column.

Source: Listing 16.2.1.1, 16.2.1.2

O:\Studies\ Prolenium\SYM 2018-02\Biometrics\Programs\Tables\xxx.sas ran on Month Day, Year at hh:mm on data from Month, Day, Year.

Table 14.1.4 – Significant Protocol Violations

Significant Protocol Violation	PN40082	Restylane Silk	Total
Did not use any study product	0 (0%)	0 (0%)	0 (0%)
Violation of inclusion/exclusion criteria	0 (0%)	0 (0%)	0 (0%)
Did not complete Visit 5 within the specified window	0 (0%)	0 (0%)	0 (0%)
Use of prohibited medications	0 (0%)	0 (0%)	0 (0%)
...			

Significant protocol violations (SPVs) are those events that exclude subjects from any of the analysis populations.

Subjects with multiple SPVs are presented under each category as appropriate (e.g., Subjects who had no post-baseline visit are not counted under SPVs related to Visit 5).

Source: Listing 16.2.1.1, 16.2.2.1, 16.2.2.2, 16.2.2.3

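### Non-inferiority is decided on the per-protocol set alone, so the planned mITT analysis cannot stop a claim even if it fails to exclude the margin

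*SAP*

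**What the plan says.** Protocol 8.1 names the deciding set, "with PP as the primary population and mITT supportive", and SAP 4 repeats this. SAP 5.5.1 is firmer: "The results for PP are considered as definitive and those for mITT as supportive".

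SAP 4 admits a subject to PP only if the subject:
- was eligible and treated;
- completed Visit 5 in window;
- had an in-window overall LFGS from the blinded evaluator at Month 2;
- had no significant protocol violation affecting the evaluation.

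SAP 5.2 draws the consequence: "There will not be missing data for the primary efficacy endpoint for the PP population based on the PP definition in Section 4". SAP 3.2 sizes the trial "assuming that 80% of randomized subjects meet the PP criteria".

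The mITT set (eligible, randomized, treated) has no follow-up condition. Its missing overall LFGS scores are multiply imputed (SAP 5.2), analysed on the same endpoint and tabulated (Table 14.2.1.2). Neither document requires the mITT interval to meet the margin or says what follows if PP and mITT disagree. SAP 5.3 compares PP with non-PP subjects on demographic and baseline characteristics only, not on outcome.

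**The concern.** The absence of missing primary data in PP is not good fortune. It arises because subjects without a usable Month 2 score are removed. Several ways out of PP before or at Month 2 can depend on how the device performed:
- A subject may withdraw at any time for any reason (Protocol 7.3.3).
- Investigator unblinding is reserved for adverse events and forces withdrawal (Protocol 7.9.10.2).
- Other fillers and lip plumpers are to be avoided (Protocol 7.4.7.2), and the example shell of Table 14.1.4 lists "Use of prohibited medications" among violations that exclude a subject from an analysis set. A disappointed subject may seek such products.

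If poor responders leave the test arm more than the control arm, those who remain look more alike across arms, and in a non-inferiority trial that favours the claim. The analysis that keeps most of these subjects is already planned but cannot block the claim.

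This point concerns the decision rule and losses up to Month 2. It does not concern the Month 6 visit condition or the eligibility condition in mITT.

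**Working it through.** **Inputs from the documents.** Error rate: "Two-sided hypothesis testing will be conducted for all inferential analyses. Resulting p-values less than 0.05 will be considered statistically significant" (SAP 5.1), that is 2.5% one-sided through the lower 95% limit. Size: "The test:control ratio of 1:1 results in 126 (63:63) PP subjects at 90% power". Assumption: "both PN40082 and Restylane Silk having an equal mean value with a common standard deviation of 0.85 for change from baseline in LFGS" (both Protocol 8.5). Sizing margin: -0.50. Randomized: 158 (79 per arm).

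**Reproducing the plan's figure.** With SD 0.85, margin 0.50 and true difference 0, 90% power needs 61 per arm by the normal formula and 62 by the exact t. At 63 per arm, power is 90.6% (t) or 91.0% (normal). 126/0.8 = 157.5, rounded up to 158. The plan's numbers hold, with 79 - 63 = 16 per arm expected outside PP.

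**False-pass rate on PP alone.** Set the true difference over all 79 per arm at exactly -0.50. Let m subjects per arm be excluded, with difference d among them (an assumption), and no other exclusions:
- PP difference = (79 × (-0.50) - m × d)/(79 - m)
- bias = PP difference + 0.50
- SE = 0.85 × √(2/(79 - m))
- false-pass rate = Φ(bias/SE - 1.96)

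Example, m = 16 and d = -1.0: PP difference = (-39.5 + 16)/63 = -0.373; bias = 0.127; SE = 0.1514; Φ(0.127/0.1514 - 1.96) = Φ(-1.12) = 13.1%.

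| m per arm | SE | d = -0.50 | d = -0.75: bias, rate | d = -1.0: bias, rate |
|---|---|---|---|---|
| 16 | 0.1514 | 2.5% | 0.063, 6.2% | 0.127, 13.1% |
| 8 | 0.1427 | 2.5% | 0.028, 3.9% | 0.056, 5.9% |
| 4 | 0.1388 | 2.5% | 0.013, 3.1% | 0.027, 3.9% |

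The first row treats every expected PP exclusion as an outcome-related loss. The 20% covers all PP criteria, including eligibility and the Visit 5 window, and the documents give no share for losses up to Month 2. The lower rows are therefore part of the answer.

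**What requiring both analyses achieves.** Simulation: 4,000 trials per scenario, 79 per arm, 16 per arm excluded, outcome-related selection in the test arm only, Month 1 to Month 2 correlation 0.7 assumed, true difference -0.50, mean-based 95% interval against -0.50. The gap is the mean change of retained minus lost test-arm subjects, in grades.

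| Loss mechanism | Gap | PP alone | Both required |
|---|---|---|---|
| Excluded, Month 2 score recorded | 0.54 / 0.95 | 11.8% / 25.6% | 2.5% / 2.7% |
| Month 2 missing, loss driven by Month 1 score | 0.38 / 0.67 | 7.6% / 14.6% | 2.2% / 2.8% |
| Month 2 missing, loss driven by unseen Month 2 score | 0.54 / 0.95 | 11.3% / 26.8% | 5.9% / 11.9% |

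With the same selection in both arms (gap 0.95), PP alone passes in 3.6%, so the bias largely cancels.

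**Power with both required (true difference 0).** The simulation with imputation gives 89.4%. A t-based simulation without imputation gives 90.1% with 79 mITT subjects per arm and 89.9% with 71. PP alone has about 90.6%.

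**The case against.** PP as the primary set is pre-specified and consistent across protocol and SAP, so this is a design weakness, not a contradiction. A reader might infer that mITT is ignored. It is not: it is analysed on the same endpoint and reported, and only its role in the decision is missing.

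A reader might also take 13% as the expected false-claim rate. The documents do not support that. The 20% counts every PP failure, the outcome difference among excluded subjects is assumed, and the bias needs losses that differ by arm. Both devices are hyaluronic acid gels with lidocaine, subjects are blindfolded for injections and the evaluator is blinded. Nothing in the documents shows differential loss. The link between prohibited products and exclusion rests partly on a table shell that SAP 6 describes as an example.

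The figures also do not describe the rule now written in SAP 5.5.1, a Hodges-Lehmann lower limit at or above -1.0. Simulated on integer scores with 63 per arm, no losses and an assumed control mean change of 1.5 to 2.0, a true -0.50 device passed that rule in every run. PP selection can add nothing at -0.50 there.

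Finally, it is tempting to say that requiring both analyses restores 2.5%. That holds only if mITT recovers the excluded outcomes. The imputation model uses treatment, site, earlier LFGS and baseline variables, so it only partly corrects loss driven by the unseen Month 2 score. Scores observed after use of another lip product stay in mITT as they are.

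All of this stands and limits the size of the point and the reach of the remedy. None of it gives mITT a place in the decision.

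**Conclusion.** The concern holds in limited form. PP alone decides, PP is selected after randomization, and a claim could stand while mITT does not exclude the margin. Against the -0.50 mean-difference margin, the false-pass rate at a true -0.50 rises from 2.5% to between 3.1% and 13.1%, depending on how many exclusions are outcome-related (4 to 16 per arm) and how much worse the difference is among them (-0.75 to -1.0). Both ranges are assumptions, and the inflation largely disappears if selection is the same in both arms. The change is worth making because it is cheap and uses an analysis already planned. The conflict between -0.50 and the SAP's -1.0 rule must be resolved first, since these rates have no meaning under the latter.

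**What to change.** First reconcile the margin to a single value across Protocol 8.2 and SAP 5.5.1. Then change SAP 5.5.1 and Protocol 8.1/8.2 to read: *Non-inferiority will be claimed only if the lower 95% confidence limit meets the pre-specified margin (the single reconciled value) in both the PP analysis and the mITT analysis with multiple imputation.* Delete the words that rank PP as definitive or primary and mITT as supportive.

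Because mITT would now help decide, the SAP should also state which standard error enters the pooling of the Hodges-Lehmann results in PROC MIANALYZE, which SAP 5.5.1 leaves open. A tipping-point sensitivity analysis would address the part that imputation cannot repair. Scores recorded after another lip product need their own stated handling, because the two-analysis rule does not correct them.

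Cost: one sentence in each document, with no new data or subjects. Power under the plan's assumptions falls from about 90.6% to about 89.4-90.1%, so the stated 90% becomes approximate.
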